VI.25 *List the data to be collected from proxy individuals including the names of any surveys, questionnaires etc. to be used. Attach data collection tools under the Relative/Proxy Data Collection Instruments category.*

Phase 2

Foa PTSD - Parent Version

Strengths and Difficulties - Parent Version

Quality of life - Parent Version

Participant Information Form

VI.26 *Is this project about pregnant women?*

No

VI.27 *Will this project involve fetuses?*

No

VI.28 *Does this project involve adult subjects who may be incompetent or have limited decision-making capacity on initial enrollment into the study?*

No

VI.32 *Does this project involve subjects whose capacity to consent may change over the course of the study?*

No

VI.37 *Does this project involve prisoners as subjects?*

No

VII.A. Project Description (A)

VII.A.1 *Where will project procedures take place (check all that apply)?*

- UIHC - UI Children's Hospital
- Other UI campus site - Westlawn
- U.S. off-campus - Blank Children's Hospital, Children's Mercy Hospital and Clinics

VII.A.2 *Is this project also being conducted by other researchers at their own sites (e.g. a multi-site collaborative project)?*

Yes

VII.A.3 *What is the UI site's role(s) for this project (check all that apply)?*

- Clinical/participating site
- Coordinating Center
- Statistical/Data Management Center

VII.A.4 *Provide specific and detailed information describing how the UI investigator will coordinate all aspects of the study, such as:*

- Name, location, and IRB of record for each site,
- Verification of IRB approval and continuing review for all sites

- *Managing variation in requirements from the IRBs or institutional policies of the different sites.*
- *Outline all activities that will occur at each participating site*

The University of Iowa researchers will participate in all aspects of data collection, management, and analysis. Because of its larger size and higher number of pediatric trauma admissions, the University of Iowa is anticipated to collect roughly two thirds of the data proposed. The UI researchers will act as the coordinating center for the multi-site collaboration, and will provide information and interim reports to Blank Children's Hospital and Children's Mercy Hospital as outlined below. The UI researchers will also ensure adherence to IRB protocol, and communicate progress with the funding agency.

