The University of Iowa researchers convene with Blank Children's Hospital and Children's Mercy Hospital researchers in monthly meetings, where such information could be discussed. If immediate attention is required, the University of Iowa team will contact the study coordinator at Blank Children's Hospital and the study coordinator at Children's Mercy Hospital to communicate the new information.
- VII.A.10** *What are collaborating site roles for this project?*
- Clinical/participating site - Blank Children's Hospital, Children's Hospital and Clinics of Minnesota, and Children's Mercy Hospital-Kansas City, 3 sites

VII.B. Project Description (B)

- VII.B.1** *Does this project involve any of the following (Check all that apply):*
- **Registry** – The collection and maintenance of data (not including biologic samples) in which: (1) the individuals in the registry have a common or related condition(s), and/or (2) the individuals in the registry are interested in being contacted for future studies by investigators other than those listed in Section II of this project. ([UI Guide](#))
 - **Repository** – The collection, storage, and distribution of human biologic samples and/or data materials for research purposes. Repository activities involve three components: (i) the collection of data and/or specimens such as blood, tissue, saliva, etc.; (ii) the storage of data or specimens, and data management function; and (iii) the sharing of data/specimens with recipient investigators other than the original investigators. (paraphrased from [OHRP](#))
 - **Expanded Access** – A process regulated by the Food and Drug Administration (FDA) that allows manufacturers to provide investigational new drugs to patients with serious diseases or conditions who cannot participate in a clinical trial. Examples of expanded access include non-protocol access to experimental treatments, including protocol exception, single-patient IND, treatment IND, compassionate use, emergency use, continued access to investigational drug, and parallel track ([ClinicalTrials.gov](#) & [FDA](#)).
 - **Clinical (or Treatment) trial** – A prospective biomedical or behavioral research study of new treatments, new drug or combinations of drugs, new devices, or new approaches to surgery or radiation therapy. (NIH and [ClinicalTrials.gov](#) & [FDA](#))

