VII.D.31 *What are the plans for the assent process for children/minors in this study? (You may choose more than one procedure if you have different child populations in your study)*

- Children/minors will sign an assent or consent document -

VII.D.36 *Provide a detailed description and rationale for each of the procedures chosen above and describe the child/minor populations to which they apply in your study.*

Phase 2

All children 10-17.2 years of age will be asked to sign an assent document. We chose to use the assent document for all participants aged 10-17.2 years because the language is simple and easy to understand, especially since the children are undergoing medical procedures in the hospital.

It was discovered on 7/15/2016 that some children who signed the assent document turned 18 at some point during the 9-month follow-up period of the study. For research subjects that were assented as children but turned 18 prior to the end of their involvement in the study, the research team will mail a re-consent instruction letter along with a new consent document to the subject. The consent document will be different than the consent document signed by the parent at initial recruitment. The documents will be mailed to research subjects via U.S. mail and provided a postage paid envelope in which to return the signed consent document to the research team.

VII.D.37 *Does the study include any form of deception (e.g., providing participants with false information, misleading information, or withholding information about certain study procedures)?*

Examples:

- *Procedure includes a cover story that provides a plausible but inaccurate account of the purposes of the research.*
- *Participants will be provided with false information regarding the particular behaviors of interest in the research.*
- *Procedures include a confederate pretending to be another participant in the study.*
- *Participants will be told that the research includes completion of a particular task, when in fact, that task will not be administered.*
- *Study is designed to introduce a new procedure (or task) that participants are not initially told about.*
- *If yes, a waiver of informed consent must be requested under question IV.3.*

No

VII.E. Project Description (E)

VII.E.1 *Will subjects be randomized?*

Yes

VII.E.1.a *Will any subjects be blinded to which study arm they have been assigned?*

No

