VII.E.2 *Describe randomization scheme/assignment including ratio such as 1:1, 2:1 etc.*

Phase 1: No randomization

Phase 2

The parent-child dyad will be randomized at a 1:1 ratio by a program developed in Microsoft Access or Excel.

VII.E.3 *Will any questionnaires, surveys, or written assessments be used to obtain data directly from subjects in this study?*

Yes

VII.E.4 *List all questionnaires, surveys, written assessments and ATTACH each one to the application. (NOTE: You are NOT prohibited from attaching copyrighted materials to this application)*

Phase 1

Two focus group questionnaires have been developed: a questionnaire for parents of injured children and a questionnaire for staff who serve these injured children. The questions for the parent interview will be equivalent to the parent focus group questions. The questions for provider key informant interviews will equivalent to those of the provider focus group. At each focus group, one study staff member will ask the questions and a second person will take notes on the answers from the participants. In the telephone interview, notes will be taken by the research staff member completing the telephone interview

Phase 2

The parent and child will be asked to answer 4 questionnaires each over the course of the study: one during hospitalization, one at 6-weeks, one at 3-months and one at 6-months post hospitalization. The 6-week, 3-month and 6-month questionnaires will be the same questionnaire.

Both parent and child will complete the baseline questionnaire and follow-up questionnaire three times.

The parent and the child questionnaires will contain the following validated questionnaires: Strengths and Difficulties Questionnaire; the Pediatric Quality of Life Inventory; CESD; Foa PTSD; Multidimensional scale of perceived social support; open family communication; and how I cope under pressure.

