Link Intervention: Intervention parents will get a 20-45 minute training on the Link for Injured Kids Program during their child's hospitalization. The training will involve viewing a Link training program on an iPad and a brief training in motivational interviewing. All Link training sessions will be audio recorded to ensure fidelity among the research team. Two weeks after hospital discharge, a packet will be

mailed to the family's home address containing the Link pocket card, trifold, and instructional DVD. At 6-weeks post-discharge, the instructor will conduct a telephone booster session with the parent trained in Link.

Trauma Education Intervention: Parents will be given the booklet "So Your Child Has Been in an Accident... An Information Booklet for Parents." This booklet will be sent again to the family's address 2-weeks after their hospital release. At 6-weeks post-discharge, the interventionist will conduct a brief telephone survey to assess the parent's perceptions regarding the Trauma Education program.

All subjects: The dyads will be asked to complete follow-up questionnaires at 6 weeks, 3-months, 6-months post hospitalization. The questionnaire will measure depressive symptoms, symptoms of post traumatic stress disorder, social support, family communication, strengths and difficulties and quality of life and asks about any mental health or community resources they may have used since the last questionnaire. The research team will e-mail a link for the parent and the child to complete their surveys as well as mail a hard copy version of the questionnaire with a cover letter explaining that the survey can be completed on paper or online and a postage paid envelope. If completed online, the questionnaires will be done electronically using REDCap, a U of I supported online survey system. A telephone call will be placed to the dyad the day the hard copy questionnaire is mailed informing the dyad of the mailing; the dyad will also have the option of completing the survey over the phone at the time of the call.

For subjects that were consented as children, but turned 18 prior to the end of their involvement in the study: after obtaining re-consent when the subject turns 18, these subjects will complete follow up questionnaires at the same intervals described for all subjects.

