- Electronic records (computer files, electronic databases, etc.) - Phase 1 All audio files, and electronic documents containing the transcription of the audio files, will be saved on the College of Public Health servers and will be password protected. Following the focus groups, the audio recorders will be placed in locked filing cabinets. Once transcription has been completed and verified, the audio files will be deleted from the audio recorders. Phase 2 The questionnaires will be completed using REDCap, an electronic online survey system supported by the U of I. A subject's study ID will be linked to the data and no identifying information will be in the follow-up surveys. Two electronic ACCESS databases will be created for tracking research subjects and for entering the baseline questionnaire. Audio recordings from external sites will be sent to the University of Iowa research team via uploading the audio files to a group SharePoint site. On the SharePoint site, each external site will have a site-specific audio file folder that is only accessible to their staff and the UI research team for the purpose of downloading files to the CPH secure servers. All audio recordings and electronic files will be stored on secure servers and only be accessible by password protected computers by the research team. Non-UI team members will be issued a HawkID in order to access the data files stored in REDCap.
 - Name - [name]
 - Title - Director of Information Technology, College of Public Health
 - University Job Classification - IT Director

X.5 *Do the confidentiality protections indicated above allow only members of the research team to access the data/specimens?*

No

X.6 *Describe*

Because the funding agency requires engagement activities of projects, we will identify partners to be consultants to the research team. Consultants may include previous study participants. These consultants may provide services by providing: feedback/suggestions about their experience with study processes, ideas about dissemination, testimonials, or collaborating on presentations. They will not be engaged in any research activities, and will not have access to any coded or identifiable data.

X.7 *Does your study meet the NIH criteria for a [Certificate of Confidentiality](#) or will you be applying for Certificate of Confidentiality?*

No

XI. Data Analysis**XI.1** *Describe the analysis methods you will use, including, if applicable, the variables you will analyze*

Phase 1

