The focus group data and key informant interviews will be analyzed using content analysis and identification of themes. Focus group and interview data will also be used to incorporate changes into the LPC for Injured Kids program.

Phase 2

If we achieve randomization, we will compare the differences in distributions between intervention and control groups using simple chi-square tests for categorical outcomes (low, medium, high levels of coing; being symptomatic for PTSD, Depression, etc.) and t-tests or Wilcoxon rank-sum tests for continuous variables depending on their normality (e.g. scores for PTSD, depression, social support).

If we do not achieve randomization (i.e. distribution of demographics are not balanced across intervention and control arms), we will also adjust for confounding using Generalized Linear Models and appropriate link functions (logit for binary outcomes, linear for continuous outcomes).

XI.2 *Provide the rationale or power analysis to support the number of subjects proposed to complete this study.***Phase 1**

The research team needs each final focus group to contain at least 6 parents or providers to get an adequate response to the focus group questions. The focus group will have potentially unpredictable schedule, either due to children in the home (parents) or heavy work load (providers) therefore we are recruiting 10 members per focus group to ensure we have at least 6 attending each focus group.

Phase 2

We conducted sample size based on testing a moderate effect size of 0.5 standard deviation comparing Trauma Education vs Link. With an alpha of 0.05, a sample size of 134 parent-child dyads in each of the arms (n=268) has 100% power to examine comparisons. We will oversample by 12% for a total n = 300.

XII. Future Research

XII.1 *Do you wish to keep any information about subjects involved with this research project so that members of the current research team may contact them in the future for your own research projects?*

No

XII.2 *Do you wish to keep any information about subjects involved with this research project so that [other researchers](#) may contact them for future research?*

No

XII.4 *Does this project involve storing any data, tissues or specimens for future research?*

No

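### Allocation is fixed only as 1:1 by an Access or Excel program, with no concealment step and no balancing by hospital, in an open multi-site trial with self-reported outcomes

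*Protocol*

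**What the plan says.** Protocol VII.E.2 asks for the randomization scheme. For Phase 2 the full answer is: "The parent-child dyad will be randomized at a 1:1 ratio by a program developed in Microsoft Access or Excel". VII.B.11 states that no separate written protocol will be submitted, so this form is the protocol.

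The surrounding text gives the setting:

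- **Blinding (VII.E.1.a).** The question "Will any subjects be blinded to which study arm they have been assigned" is answered no.
- **Sites.** VII.A.10 lists, besides UI, "Clinical/participating site - Blank Children's Hospital, Children's Hospital and Clinics of Minnesota, and Children's Mercy Hospital-Kansas City, 3 sites". VII.A.4 says that "the University of Iowa is anticipated to collect roughly two thirds of the data proposed" and makes UI the coordinating center. VI.14 has Children's Mercy joining in year 3.
- **Recruitment (VII.D.29, VII.D.30).** The research team reviews the record, picks a time on the day of discharge or another suitable moment, gives the orientation test, and obtains consent. If the moment is inconvenient, the team member leaves and comes back.
- **Order of procedures (VII.E.6).** Consent, contact details and baseline questionnaires are described first, then the arm-specific procedures. Link training takes place during the hospital stay. Baseline data are taken on iPad or paper and entered into databases once staff are back in their offices.
- **Systems.** X.4: "Two electronic ACCESS databases will be created for tracking research subjects and for entering the baseline questionnaire". It also says: "Non-UI team members will be issued a HawkID in order to access the data files stored in REDCap". VII.E.6 says of follow-up completed online that "the questionnaires will be done electronically using REDCap, a U of I supported online survey system".
- **Analysis (XI.1).** Chi-square tests and t-tests or rank-sum tests are planned. Models with adjustment are added under this condition: "If we do not achieve randomization (i.e. distribution of demographics are not balanced across intervention and control arms". Hospital is not named as a covariate.

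**The concern.** Concealment matters most when three things coincide: the recruiter has discretion, the trial is open, and the outcome is reported by people who know their arm. All three hold here. A team member who knows or can guess the next arm can, even without intent, come back later to a family that looks unsuited to a 20-45 minute training, or present the study with more or less energy. The arms then differ in prognosis from the start.

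The planned analysis would not repair this. Unadjusted tests compare the arms as they stand. The fallback adjustment is triggered by demographics, whereas selection on distress, family engagement or injury burden need not show there. VIII.3 provides for no periodic review of combined data, so no outside check on allocation is described either.

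The timing adds to the difficulty. The arm has to be known at the bedside, because Link training is given in hospital, while baseline data may reach the database only later. With an office-software program, the assignment would be looked up before the visit, fetched during it, or carried by the team. The protocol does not say which, and only some of these conceal it.

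Hospital balance is the lesser issue. Sites differ in size and calendar time, and nothing beyond the 1:1 ratio is stated.

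**Working it through.** **1. The plan's own figure (XI.2).** Inputs: effect 0.5 SD, alpha 0.05 (two-sided assumed), 134 dyads per arm.

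- SE = sqrt(2/134) = 0.122 SD.
- Power = Φ(0.5/0.122 − 1.96) = Φ(4.09 − 1.96) = 98.4%. The protocol states 100%, so the figure is reproduced to within 2 points.
- 268 × 1.12 = 300.2, which matches the stated total of 300.

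The point does not depend on these figures; they supply the SE used below.

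**2. Foreknowledge (assumed inputs).** Let s be the difference between arms in the share of dyads that steering has moved, and d their difference in prognosis in SD units. Bias = s × d. The document gives neither, so a range is used.

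| s | d | Bias (SD) | Bias / SE | Two-sided rejection rate if no true effect |
|---|---|---|---|---|
| 5% | 0.5 | 0.025 | 0.20 | 5.5% |
| 10% | 0.5 | 0.05 | 0.41 | 6.9% |
| 10% | 1.0 | 0.10 | 0.82 | 13.0% |

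The last column is Φ(−1.96 + r) + Φ(−1.96 − r), with r = bias/SE. Against the 0.5 SD target, the bias is 5% to 20% of the effect sought.

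**3. Chance imbalance by hospital.** This assumes simple randomization, since no blocking or stratification is stated. VII.A.4 implies about 200 of 300 dyads at UI and 100 elsewhere; any further division is assumed. From Binomial(n, 0.5), the two-sided chance of a 60:40 split or worse is:

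| Dyads at site | Chance |
|---|---|
| 200 | 0.6% |
| 100 | 5.7% |
| 50 | 20% |
| 40 | 27% |

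The chance that at least one site reaches 60:40 is 6% for sites of 200/100, 37% for 200/50/50 and 62% for 200/34/33/33.

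**4. What that imbalance does to the comparison.** With sites of 200 and 100, simulation gives a between-arm difference in the smaller site's share of at most about 0.107 in 95% of trials. The formula agrees: 1.96 × sqrt(1/3 × 2/3 × 2/150) = 0.107. Multiply by an assumed outcome difference between sites:

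- 0.2 SD × 0.107 = 0.02 SD
- 0.5 SD × 0.107 = 0.05 SD

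Overall power also barely moves: 98.4% at 134:134 and 98.2% at 118:150. Lopsided small sites are therefore quite likely under simple randomization, but their effect on the arm comparison is small.

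**The case against.** The strongest reply is that much of the worry rests on silence. A program built in Access can be held centrally, can hide the sequence, and can block or stratify by hospital. Custody of the sequence may be set out in a procedure that is not shown. X.4 puts electronic files on secure servers behind passwords. Eligibility is tied to the record, the care team and a scored orientation test, screen failures are logged, and VII.E.6 describes baseline questionnaires before the arm-specific procedures. These features narrow the room for steering.

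Much of that stands, and it rules out several stronger readings that a reader might infer:

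- **That recruiters can open, re-run or read ahead in the file, or that each site has its own.** The protocol does not say so. It also does not tie the two Access databases to the randomization program.
- **That allocation is simple randomization.** This is an assumption of the calculation, not a statement in the protocol.
- **That nobody is blinded.** VII.E.1.a covers subjects only; staff and analysts are not addressed.
- **That REDCap is a ready allocation system at every site.** It appears only as a survey and data system. Its use at Blank, which has its own IRB submission, is not described.
- **That hospital imbalance seriously threatens the result.** Chance imbalance is random error, and step 4 shows it to be small.

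What does not stand is that nothing needs changing. VII.E.2 asks for the scheme and answers with a tool, leaves two tools open, and states no safeguard. How a recruiter obtains an assignment is a matter for the protocol more than for an analysis plan. Server passwords do not help where the team that recruits is also the team with access.

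**Conclusion.** The point holds as a weakness of the stated method, not as evidence that allocation was compromised. In an open trial with recruiter discretion and self-reported outcomes, a 1:1 ratio from an Access or Excel program, with no concealment step, does not protect against foreknowledge of the next arm.

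The possible bias of about 0.03-0.10 SD rests wholly on assumed steering and prognosis. It is below one standard error, but at the upper end it would raise the false-positive rate from 5% to about 13%. Hospital imbalance is secondary at about 0.02-0.05 SD, assuming simple randomization, sites of 200 and 100, and outcome differences of 0.2-0.5 SD between them.

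A change is worth making because it is cheap and because selection at entry cannot be reliably corrected afterwards. XI.1's description of demographic imbalance as a failure of randomization is a separate matter of analysis wording. It bears here only in showing that the fallback adjustment is not aimed at selection or at hospital.

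**What to change.** Replace the Access or Excel program in VII.E.2 with the following:

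1. **Sequence.** Generated and held by the UI coordinating center on a server that recruiters cannot read. REDCap may serve if its installation supports allocation and every enrolling site can reach it.
2. **Balance.** Stratified by hospital, in permuted blocks of varying size. For scale, blocks of 4 would hold the difference between arms at each hospital to 2 dyads at most.
3. **Release.** Each assignment is revealed only after consent and after both baseline questionnaires are completed, on iPad or paper. Database entry need not come first, so bedside training is not held up.
4. **Analysis.** Hospital is included in the main comparison of the arms, whether or not demographics look balanced.
5. **Transition.** VII.D.36 reports a July 2016 finding about enrolled children who turned 18 during follow-up, so enrolment had begun. Apply the change from a stated date and report the two allocation periods. For the earlier period, record who held the program and when assignments were seen.

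The cost is one-time set-up, an IRB modification and documentation of the switch. Recruiters need a way to reach the server from the bedside, where iPads are already used. If the existing program already meets items 1 to 3, stating so in VII.E.2 is enough for those items.

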If an online or mailed questionnaire is not returned within 7 days the research team will attempt to contact the dyad by phone 12 times (for each follow-up period) to remind them to complete the questionnaire or to make arrangements for the questionnaire to be completed at an already scheduled follow-up appointment at the hospital. For 6-week questionnaire, they will be contacted 12 times up to 6 weeks following their eligibility to complete that questionnaire. For 3-month questionnaire, they will be contacted 12 times up to 3 months following their eligibility to complete that questionnaire. For 6-month questionnaire they will be contacted 12 times up to 6 months following their eligibility to complete that questionnaire. After a month of no response for any survey timepoint, we will resend the package or online link. If a dyad does not complete the 6-week questionnaire, they will still be asked to complete the 3-month and 6-month questionnaires.

The research team will complete the medical record abstraction within 12 months of receiving the medical record consent. The data collected from the medical record includes measures of injury severity, the type of injury the child sustained, external cause of injury, length of stay, diagnostic procedures, Glasgow Coma Scale measures, comorbidities, and initial vital signs and all discharge codes.

VII.E.7 *Will you attempt to recontact subjects who are lost to follow-up?*

No - those lost to followup will not be recontacted

VII.E.9 *Will subjects be provided any compensation for participating in this study?*

Yes

VII.E.10 *Cash*

No

VII.E.11 *Gift Card*

No

VII.E.12 *Check*

Yes

VII.E.13 *Who will be providing the research compensation check to the subject?*

Accounting Services directly via the e-Voucher system

VII.E.16 *Other*

Yes

VII.E.17 *Describe:*

Phase 1: A light meal will be provided to all focus groups. For the parent focus groups, on-site child care will also be provided.

Phase 2: None

VII.E.18 *If you plan to compensate subjects using cash, checks or cash equivalent does your unit have a [Cash Handling Procedure](#) in place that has been approved by Accounting Services?*

Yes

VII.E.19 *Describe the compensation plan including*

- *Compensation amount and type per visit*
- *Total compensation*
- *Pro-rating for early withdrawal from study*

Phase 1

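### Must the plan change because the Link booster and the first follow-up form both fall at 6 weeks, and resource use is asked over a variable period?

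*Protocol*

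**What the plan says.** Section VII.E.6 gives the Link arm a second contact: "At 6-weeks post-discharge, the instructor will conduct a telephone booster session with the parent trained in Link". At the same time point in the Trauma Education arm, "the interventionist will conduct a brief telephone survey" about how the parent viewed that programme. The outcome schedule is common to both arms: "The dyads will be asked to complete follow-up questionnaires at 6 weeks, 3-months, 6-months post hospitalization". Forms go out by e-mail link and by post. A telephone call is made on the day of posting, and "the dyad will also have the option of completing the survey over the phone at the time of the call".

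Reminders have a limit for each wave. For the first, "For 6-week questionnaire, they will be contacted 12 times up to 6 weeks following their eligibility to complete that questionnaire"; for the second, "For 3-month questionnaire, they will be contacted 12 times up to 3 months following their eligibility to complete that questionnaire"; the 6-month form has the matching 6-month limit. A dyad that misses the 6-week form is still sent the later ones. Section VII.E.4 says that one and the same form serves all three waves. Section VII.E.6 summarises its resource item as one that "asks about any mental health or community resources they may have used since the last questionnaire".

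Section VII.D.36, on assent, refers to follow-up lasting 9 months when it explains that some children turn 18 during the study. Section VII.E.6 deals with them: "after obtaining re-consent when the subject turns 18, these subjects will complete follow up questionnaires at the same intervals".

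**The concern.** Three features look like faults in the measurement plan.

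- **Booster and outcome share a due date.** With no stated order and a long reminder period, the 6-week Link scores may mix answers reflecting the hospital training and mailed packet alone with answers reflecting the programme including its booster. The comparator's call is not a booster. Section XI.1 names no primary time point, so the 6-week wave cannot be set aside as secondary.
- **The recall period varies.** Counting from the preceding form makes the period depend on when that form came back and whether it came back at all. Access to mental health is among the possible outcomes in section 1.5, and the simple tests in section XI.1 take no account of the period covered.
- **The follow-up length does not fit.** Nine months agrees with neither the schedule nor the reminder limits.

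At stake would be the meaning of the 6-week effect, and whether resource use can be compared between children and between waves.

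**Working it through.** **Follow-up length.** The last form is due at 6 months (sections 1.4, VII.E.4 and VII.E.6). Adding its reminder limit gives 6 + 6 = 12 months. Neither equals 9. The one route to 9 is the age cap in section VI.13: 18 years minus 17 years 3 months is 9 months. The document does not say that this is where the figure comes from. The 12 months is derived from a limit on reminders and is nowhere stated as a follow-up length.

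**Contact periods, in weeks from discharge.** One month is 365.25 / 12 / 7 = 4.348 weeks, so 3, 6 and 12 months are 13.04, 26.09 and 52.18 weeks. Eligibility for a form is taken to begin on its due date.

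| Form | Due | Reminders end |
|---|---|---|
| 6-week | 6 | 6 + 6 = 12 |
| 3-month | 13.0 | 26.1 |
| 6-month | 26.1 | 52.2 |

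**Booster.** If the booster is given on time at week 6, a 6-week form may precede it or follow it by up to 12 − 6 = 6 weeks. The 3-month form is due 13.0 − 6 = 7.0 weeks after the booster and the 6-month form 26.1 − 6 = 20.1 weeks after it. Only the first of three waves can straddle it.

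**Recall period**, assuming that each form is completed between its due date and the end of reminders:

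| Form | Earlier forms | Shortest | Nominal | Longest |
|---|---|---|---|---|
| 3-month | 6-week done | 13.04 − 12 = 1.0 | 13.04 − 6 = 7.0 | 26.09 − 6 = 20.1 |
| 3-month | 6-week missed | 13.0 | – | 26.1 |
| 6-month | 3-month done | 26.09 − 26.09 = 0 | 26.09 − 13.04 = 13.0 | 52.18 − 13.04 = 39.1 |
| 6-month | only 3-month missed | 26.09 − 12 = 14.1 | – | 52.18 − 6 = 46.2 |
| 6-month | both missed | 26.1 | – | 52.2 |

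Where no earlier follow-up form exists, the period also includes the short time from baseline to discharge. These are corner cases. Zero weeks needs a 3-month form returned on its last reminder day and the 6-month form completed that same day. Fifty-two weeks needs both earlier forms missed and the last one returned at its limit.

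**What the present anchor gives.** Let the forms be completed at weeks t1, t2 and t3. The periods add to t1 + (t2 − t1) + (t3 − t2) = t3. If the first form is missed, t2 + (t3 − t2) = t3 again. Total use up to the last form therefore covers the same span whichever earlier form was missed, without gap or overlap.

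**What a start at discharge would give.** The periods would be 13.0 to 26.1 weeks and 26.1 to 52.2 weeks, each at most two-fold. Nominal recall would rise from 7 to 13 weeks at the 3-month form and from 13 to 26 weeks at the 6-month form, and earlier use would be reported again at each wave.

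**What seeking the form before the call would give.** With the call left at 6 weeks, dyads who answer readily would move to before the booster and slow ones would stay after it. Booster status at the 6-week wave would then follow responsiveness. Greater use of telephone completion would also move self-completed symptom scales towards interviewer administration, in a trial where section VII.E.1.a says that subjects are not blinded.

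**The case for a change.** The best case for a change is that call order and item wording are data-collection procedures, which this document fixes. A later analysis plan could classify forms as before or after the booster only if completion and call dates are kept. It could never alter when the answers were given. The document does not say that those dates are kept, and putting the form before the call looks cheap.

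Part of this stands. No order is stated, and recording both dates is sensible practice. But the reminder rules in section VII.E.6 (action after 7 days, resending after a month, limits by wave) can hardly be run without tracking sending and return, and section X.4 provides a database for tracking subjects. Logging the call date beside these is routine conduct. Given the dates, order and period covered can be described, and use per week covered is an analysis detail that a statistical analysis plan can hold.

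The rest does not carry. Link is compared with Trauma Education as a package, and the aim in section 1.5 is exploratory. Mixed timing at one wave is a caveat on interpretation, not an error in the comparison. The proposed order is not shown to reduce the mixing.

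**Conclusion.** No change to the plan is needed.

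- **Call order:** a gap of operational detail in one wave of three. The comparison of assigned programmes stays valid if return times are similar by arm, and the 3- and 6-month forms are due after the booster. The 6-week result should be read as the programme at about that time, with the booster given to some and still to come for others.
- **Recall anchor:** a fair trade-off. It gives short nominal recall (7 and 13 weeks) that adds up without overlap, at the price of unequal periods within the bounds above. A start at discharge reverses that exchange and is not clearly better.
- **Nine months:** a clerical slip in a passage on assent. Re-consent covers children who turn 18, and no analysis uses the figure. It can be tidied when the text is next edited.

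This rests on the booster being given on time, on return times not differing materially by arm, and on the resource item reading as section VII.E.6 summarises it, with families counting from the last form they completed. The questionnaires themselves are not shown. Typical return times are not given, so the ranges are limits rather than expected values, and no bias is claimed.
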